2 STUDY OBJECTIVES AND ENDPOINTS

OBJECTIVES	ENDPOINTS
Primary	Efficacy endpoint:
To evaluate the efficacy of ASN002 in subjects with moderate to severe chronic hand eczema (CHE) based on hand modified Total Lesion Symptom Score (mTLSS)	
 Percent change from baseline in hand mTLSS at Week 16
Secondary	Efficacy endpoints:
To evaluate the efficacy of ASN002 in subjects with moderate to severe CHE.	
 Change from baseline in hand mTLSS at Weeks 4, 8, 12, 16 Percent change from baseline in hand mTLSS at Weeks 4, 8, and 12 Proportion of subjects achieving at least a 2-grade reduction from baseline to clear (0), almost clear (1) or mild (2) in hand PGA at Weeks 4, 8, 12 and 16 Proportion of subjects achieving a hand PGA of clear (0) or almost clear (1) at Weeks 4, 8, 12 and 16 Change from baseline in hand PGA at Weeks 4, 8, 12 and 16

PPD	STATISTICAL ANALYSIS PLAN, Version Final 1.0
Protocol Number: ASN002AD-202 V6.0	Sponsor: Asana BioSciences, LLC

OBJECTIVES	ENDPOINTS
	
 • Change and percent change from baseline in Hand Eczema Severity Index (HECSI) at Weeks 4, 8, 12 and 16 • Time to response relative to baseline (based on hand PGA) • Actual hand Patient Global Assessment (PaGA) at Weeks 4, 8, 12 and 16 • Change from baseline in hand Dermatology Life Quality Index (DLQI) at Weeks 2, 4, 8, 12 and 16 • Change and percent change from baseline in pain visual analog scale (VAS) at Weeks 4, 8, 12 and 16
	Safety endpoints:
To evaluate the safety and tolerability of ASN002 in subjects with moderate to severe CHE	
 • Number of Treatment Emergent Adverse Events (TEAEs) • Number of drug-related TEAEs • Proportion of subjects withdrawing for worsening of their CHE at Weeks 4, 8, 12, and 16 • Changes from baseline in vital signs • Change from baseline in ECG • Change from baseline in safety laboratory tests
	Pharmacokinetic endpoints:
To quantify the plasma concentrations of ASN002 in subjects with moderate to severe CHE	
 • Measurement of plasma concentrations of ASN002 in all subjects receiving ASN002 treatment.
Exploratory	Exploratory endpoints:
To evaluate pharmacodynamic (PD), biomarkers and skin microbiome analysis for evidence of drug activity in subjects with moderate to severe CHE	
 • Change from baseline in PD, biomarkers and skin microbiome analysis at Weeks 4 and 16.

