3.3 Treatment

The treatment groups are:

- Part A: ASN002 40 mg (16-week treatment); Part B: ASN002 40 mg (16-week treatment)
- Part A: ASN002 80 mg (16-week treatment); Part B: ASN002 80 mg (16-week treatment)
- Part A: Placebo (16-week treatment); Part B: ASN002 80 mg (16-week treatment)

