14.1 Adverse Events

Adverse events (AEs) will be coded according to the Medical Dictionary for Regulatory Activities (MedDRA), Version 21.0.

Treatment emergent adverse event (TEAE) is any condition that was not present prior to treatment with the study product but appeared following first dose in Part A, was present at treatment initiation but worsened during treatment, or was present at treatment initiation but resolved and then reappeared while the individual was on treatment (regardless of the intensity of the AE when the treatment was initiated). See [Appendix 2](#) for handling of completely or partially missing dates for AEs. In the case where it is not possible to define an AE as treatment emergent or not, the AE will be classified as treatment emergent. AEs will be considered in Part A or Part B depending on the onset date – if the AE onset date was on or before week 16 the AE will be considered as a Part A AE. If the AE had an onset after week 16 the AE will be considered as a Part B AE. AEs emerged in part A and last into part B would be reported in both parts A and B and be noted in the part B report for these AEs which are reported twice.

An overall summary table of adverse events will be provided. The number of events and the number and percentage of subjects who experienced AE, TEAE, TEAE by greatest reported relationship, TEAE by relationship, TEAE by highest reported severity, TEAE by severity, related TEAE by highest reported severity, related TEAE by severity, serious AE, serious TEAE, serious TEAE by greatest relationship, TEAE and related TEAE leading to study drug discontinuation, TEAE and related TEAE leading to study discontinuation, TEAE and related TEAE leading to treatment interruption and AE leading to death will be presented as well as TEAE of clinical interest.

TEAE of clinical interest are:

- Thrombotic events

PPD	STATISTICAL ANALYSIS PLAN, Version Final 1.0
Protocol Number: ASN002AD-202 V6.0	Sponsor: Asana BioSciences, LLC

- Serious infection
- Malignancy and lymphoproliferative disorders
- Gastrointestinal perforation
- Hypersensitivity
- Anemia
- Neutropenia
- Lymphopenia
- Liver enzyme elevation
- CPK and lipid elevation

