Placebo patients from Part A cross over to ASN002 80 mg treatment during Part B. The treatment columns will be presented as ASN002 40 mg, ASN002 80 mg, Placebo crossed-over to ASN002 80 mg and combined ASN002 80 mg (ASN002 80 mg and Placebo crossed-over to ASN002 80 mg combined).

Study Treatment Full Names	Study Treatment Output Names
ASN002 40 mg	ASN002 40mg
ASN002 80 mg	ASN002 80mg
Placebo crossed-over to ASN002 80 mg	Placebo/ASN002 80mg
ASN002 80mg and Placebo crossed-over to ASN002 80 mg combined	Combined ASN002 80mg

3. Combined Output for Part A and B:

Placebo patients from Part A cross over to ASN002 80mg treatment during Part B.

For the analysis by treatment and visit, (ASN002 80mg and placebo/ASN002 80mg will be anchored by the first dose time) and presented as follows.

Study Treatment Full Names	Study Treatment Output Names
ASN002 40 mg	ASN002 40mg
ASN002 80 mg	ASN002 80mg
ASN002 40 mg and ASN002 80 mg	ASN002 Overall
Placebo	Placebo/ASN002 80mg
ASN002 80mg and Placebo crossed-over to ASN002 80 mg combined	Combined ASN002 80mg

PPD	STATISTICAL ANALYSIS PLAN, Version Final 1.0
Protocol Number: ASN002AD-202 V6.0	Sponsor: Asana BioSciences, LLC

Appendix 2: Algorithm for Imputation of Start/End Date of Adverse Events and Prior/Concomitant Medications

Event Start Date Imputation

- Imputation of event end date should be done before imputation of event start date.
- Completely missing: Impute to the first study treatment date.
- Missing day and month: Impute to January 1st, unless year is the same as year of first study treatment dose then impute to the first study treatment date.
- Missing day: Impute to the 1st of the month, unless month and year are the same as month and year of first study treatment dose then impute to the first study treatment date.
- If imputed event start date is after event end date (imputed or not), set the event start date to the imputed event end date.

Event End Date Imputation

- Completely missing (and not flagged as “ongoing”): Impute to the last contact date.
- Missing day and month: Impute to December 31st, unless year is the same as last contact date then impute to the last contact date.
- Missing day: Impute to the last day of the month, unless year and month are the same as year and month of last contact date then impute to the last contact date.

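### SAP 14.1 allocates AEs to Part A or Part B by onset date but then reports ongoing Part A events in both parts, so unchanged placebo-onset events can enter the ASN002 80 mg counts

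*SAP*

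**What the plan says.** SAP 14.1 gives an allocation rule in two halves: "if the AE onset date was on or before week 16 the AE will be considered as a Part A AE", and "If the AE had an onset after week 16 the AE will be considered as a Part B AE". Read alone, these put every event in exactly one part.

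The next sentence departs from that: "AEs emerged in part A and last into part B would be reported in both parts A and B", and such events are to "be noted in the part B report for these AEs which are reported twice". The only condition is that the event continues. Worsening or recurrence in Part B is not required.

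Four other provisions determine what follows from this:

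- **Anchor.** The TEAE definition in SAP 14.1 covers a condition that "appeared following first dose in Part A". For subjects randomised to placebo, that dose is placebo.
- **Switch.** Under SAP 3.3 and footnote s of the Schedule of Events, placebo subjects start ASN002 80 mg at the Week 16 visit.
- **Columns.** SAP 14 presents AEs separately by part, grouped by initial assignment. SAP 6.7 and Appendix 1 label the crossovers 'Placebo/ASN002 80mg' in Part B. Appendix 1 also pools them with the continuing 80 mg arm ("combined ASN002 80 mg (ASN002 80 mg and Placebo crossed-over to ASN002 80 mg combined").
- **Endpoints.** The number of TEAEs and the "Number of drug-related TEAEs" are secondary safety endpoints in SAP 2 and Protocol 3.

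**The concern.** The carry-over sentence lets an event enter an 80 mg summary although it started before the subject had taken any ASN002 and did not change afterwards. The TEAE definition does not screen it out, because the anchor is not reset at the first active dose.

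The same applies to related events. Investigators rate causality (Protocol 8.7.4.1) and stay blinded throughout (Protocol 6.3.1), so a placebo-onset event can be rated possibly related. SAP 14.1 then classes it as treatment-related, as it does any event of unknown relationship.

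Appendix 2 of the SAP widens the route. An event with a completely missing end date, even if not flagged as ongoing, has its end date imputed to the last contact. For a subject followed into Part B, a placebo-period event with no recorded end then counts as lasting into Part B.

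Safety is summarised without inferential statistics (Protocol 9.3.3), so these descriptive counts are the safety evidence. Several TEAEs of clinical interest in SAP 14.1, such as anaemia or liver enzyme elevation, could plausibly persist across Week 16. In the continuing 40 mg and 80 mg arms the same rule reports one event in both parts, so the two sets of counts could not be added.

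**Working it through.** **Following one event through the rules.** A placebo subject has an AE of constant severity that starts in Week 12 and is still present in Week 20.

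1. Onset-date rule: Part A only.
2. Carry-over sentence: Part A and Part B.
3. TEAE definition: it started after the first Part A dose, so it is a TEAE.
4. Part B column: 'Placebo/ASN002 80mg', and also 'Combined ASN002 80mg' if that layout is used for AEs.

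Steps 1 and 2 disagree, and nothing in either document removes the event at steps 3 or 4.

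**The switch day.** The Part A rule includes Week 16 itself, but crossovers take their first 80 mg dose at that visit. An AE that starts later that day, after the active dose, is a Part A event in the placebo column. As written, only the carry-over sentence brings it into Part B, and only if it lasts.

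**Size.** The plan states no figure here, so there is nothing to reproduce. The following is an illustration.

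Inputs:
- Crossovers: SAP 5.1 gives up to 35 per group and 25-30% dropout. 35 × 0.75 = 26.25 and 35 × 0.70 = 24.5, so about 25. The continuing 80 mg arm is taken as the same size.
- b, the share of subjects with an AE newly arising in Part B: assumed 20% or 40%.
- q, the share of crossovers with an unchanged placebo-onset AE ongoing at Week 16: assumed 5% to 30%, independent of b.

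Formulas for the displayed percentage of subjects, if carried-over events stay in the numerators:
- Crossover column: b + q − bq
- Combined column: the average of that value and b. This adds carry-over from placebo only.

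| q | Subjects carried (25q) | Crossover, b = 20% | Combined, b = 20% | Crossover, b = 40% | Combined, b = 40% |
|---|---|---|---|---|---|
| 5% | 1.25 | 24% | 22% | 43% | 41.5% |
| 10% | 2.5 | 28% | 24% | 46% | 43% |
| 20% | 5 | 36% | 28% | 52% | 46% |
| 30% | 7.5 | 44% | 32% | 58% | 49% |

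Worked cell: with q = 20% and b = 40%, 0.40 + 0.20 − 0.08 = 0.52. Of 25 crossovers, 13 are shown instead of 10. The extra 3 (25 × 0.20 × 0.60) have only a placebo-onset event.

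If subjects with a carried-over event are also more likely to have a new one, the percentages rise by less. Event counts rise by every carried event in any case.

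**The case against.** The case for leaving the rule alone has five parts.

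- **The double reporting is disclosed.** The SAP promises a note. It does not say whether this is a footnote, a flag or a separate line, and table layouts are in another document (SAP 5). A reader might infer that the duplicates certainly remain in the numerators without being marked. The text does not establish that. It says that they are reported in both parts and noted, and it does not say that they are taken out.
- **The crossover label keeps the origin visible.** This stands for 'Placebo/ASN002 80mg'. It fails for the Combined column, but Appendix 1 applies its layouts only where applicable, and SAP 14 groups AEs by initial treatment. Use of the Combined column for AEs is possible, not certain.
- **Protocol 9.3.3 speaks of the prevalence of TEAEs.** That could justify showing events present during a period. It does not supply a double-reporting rule, settle the conflict within SAP 14.1, or justify mixing inherited and new events in one count.
- **The consequences are limited.** A reader might infer that the placebo-controlled safety comparison is biased. It is not inflated by carry-over, which adds only to Part B. Part B is supportive (Protocol 6.3.1), the error overstates harm on drug rather than hiding it, and the randomised 80 mg arm supplies its own 80 mg data. No passage plans to add Part A and Part B rates. All of this stands.
- **Counting only from the first Part B dose is not simple.** Protocol 8.7.5 lists an onset date, not a time, so switch-day onsets cannot be placed from dates alone. This stands, and the fix has to deal with it.

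**Conclusion.** The point holds as a contradiction within SAP 14.1 that should be resolved before Part B is tabulated. As written, unchanged placebo-onset events can enter the Part B TEAE and related-TEAE counts for subjects then on 80 mg. The misattribution is clearest in the Combined column, if AE tables use it.

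On the assumed rates, the overstatement is 3 to 24 percentage points in the crossover column and 1.5 to 12 in the Combined column. These ranges rest on about 25 subjects per group, independence of carried-over and new events, and carried-over events staying in the numerators. Neither the carry-over share nor the new-event share comes from the documents, so no single cell of the table is an estimate for this trial.

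The documents do not support reading this as a concealed error or as a threat to the Part A comparison. It affects how supportive, descriptive 80 mg safety data will read, and it is cheap to correct.

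**What to change.** Amend SAP 14.1 as follows.

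1. Replace the two conflicting sentences with one rule: Part B TEAE counts and percentages include only AEs with onset, worsening or recurrence on or after the first Part B dose. For crossovers, judge treatment emergence in Part B against the first ASN002 dose.
2. Show AEs ongoing from Part A without worsening on a separate line or listing, such as 'ongoing at Part B entry', outside the Part B numerators. This keeps the prevalence information and gives the promised note a defined form.
3. State a rule for onsets on the Week 16 dosing day. One option is to count them in Part B unless a recorded time shows onset before the dose.
4. State whether AE tables use the Combined column, and which part shows a Part A-onset AE that leads to interruption or discontinuation in Part B.

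The cost is SAP wording and a change to the AE derivation flag. The downsides are that worsening must be derived from recorded severity changes, and that same-day onsets need either an onset time or the default rule.

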14.2 Clinical Laboratory

Descriptive statistics will be presented for data related to chemistry, hematology and quantitative urinalysis. Change from baseline values will be presented for each post-baseline assessment. Frequencies and percentages for each result will be provided for qualitative urinalysis data.

Shift tables from baseline to each post-baseline visits describing shifts to abnormality will be provided as well. Only subjects with a baseline result and a result at the specified visit for the parameter will be considered.

Separate listings of all data for chemistry, hematology, urinalysis, serology and pregnancy test will be provided.

In addition, separate listings of data for chemistry, hematology, and urinalysis will be provided for each parameter where a subject had at least one abnormal result.

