4.4.1 Interruption criteria

A subject who meets either of the below criteria will have the study drug interrupted until laboratory retesting is performed and/or event resolution.

- neutrophils $> 0.5 \times 10^3 / \mu\text{L}$ but $< 1 \times 10^3 / \mu\text{L}$;
- platelet count $> 50 \times 10^3 / \mu\text{L}$ but $< 100 \times 10^3 / \mu\text{L}$;
- lymphocytes $> 0.2 \times 10^3 / \mu\text{L}$ but $< 0.5 \times 10^3 / \mu\text{L}$;
- CPK $> 10 \times \text{ULN}$;
- an infection requiring IV treatment with antiviral, antibiotic, antiprotozoal, antiparasite or requiring oral medications of those longer than 2 weeks;
- AST/ALT $> 5 \times \text{ULN}^*$.

*Decision to restart the medication following any laboratory abnormality described above will be made in consultation with the study sponsor and medical monitor.

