ALT = alanine aminotransferase; anti-HBc = antibody to hepatitis B core antigen; AST = aspartate aminotransferase; β -hCG = β -human chorionic gonadotropin; BUN = blood urea nitrogen; CPK = Creatine phosphokinase; CRP = C-reactive protein; FSH = follicle-stimulating hormone; GGT = gamma-glutamyl-transferase; HBsAg = hepatitis B surface antigens; HBV = hepatitis B virus; HCT = hematocrit; HCV = hepatitis C virus; HDL = high-density lipoproteins; Hgb = hemoglobin; HIV = human immunodeficiency virus; LDH = lactate dehydrogenase; LDL = low-density lipoproteins; MCH = mean corpuscular hemoglobin; MCHC = mean corpuscular hemoglobin concentration; MCV = mean corpuscular volume; MPV = mean platelet volume; PLT = platelets; PPD = purified protein derivative; RBC = red blood cell (count); ULN = Upper Limit of Normal; WBC = white blood cell (count).

Subjects who do not qualify to participate in the study due to a screening laboratory value abnormality can repeat the test once within the original screening time window without resulting in screen failure, if the investigator believes there is a reasonable possibility that the subject would be eligible if re-tested.

If deemed appropriate by the investigator, clinically significant findings in clinical laboratory testing will exclude a subject from study participation. Any clinically significant findings will be reported as an AE.

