5.5 Descriptive Statistics

All continuous variables will be summarized by presenting the number of subjects, mean, standard deviation, median, minimum, and maximum. Categorical variables will be presented as frequencies and percentages. Summary tables will be presented by treatment and visit, when applicable.

Change from baseline will be calculated as:

Assessment value at post-baseline visit X – baseline value.

Percent change from baseline will be calculated as:

$$(\text{Assessment value at post-baseline visit X} - \text{baseline value}) / \text{baseline value} \times 100.$$

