14.4 Electrocardiogram (ECG)

Descriptive statistics will be presented for data related to ECGs (heart rate, RR interval, PR interval, QRS duration, QT interval and QTcF interval). Change from baseline values will be presented for each post-baseline assessment.

Shift tables from baseline to each post-baseline visit and to each timepoint describing shifts to abnormality will be provided for overall interpretation. Only subjects with a baseline result and a result at the specified visit will be considered.

A listing of ECG assessments will be provided. In addition, a listing will be provided for each parameter where a subject had at least one abnormal result.

PPD	STATISTICAL ANALYSIS PLAN, Version Final 1.0
Protocol Number: ASN002AD-202 V6.0	Sponsor: Asana BioSciences, LLC

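### SAP 14.2 plans no per-arm count of subjects who met the protocol's laboratory limits for interruption (4.4.1) or permanent discontinuation (4.4.2)

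*SAP*

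**What the plan says.** **Limits.** Protocol 4.4.1 lists numeric interruption limits for neutrophils, platelets, lymphocytes, CPK and AST/ALT, and states: "A subject who meets either of the below criteria will have the study drug interrupted until laboratory retesting is performed and/or event resolution". Protocol 4.4.2 lists lower limits for neutrophils, lymphocytes and platelets that end the subject's participation.

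**Laboratory outputs.** SAP 14.2 states: "Descriptive statistics will be presented for data related to chemistry, hematology and quantitative urinalysis". SAP 5.5 defines the content: "All continuous variables will be summarized by presenting the number of subjects, mean, standard deviation, median, minimum, and maximum". SAP 14.2 adds change from baseline, frequencies for qualitative urinalysis, and shift tables: "Shift tables from baseline to each post-baseline visits describing shifts to abnormality will be provided as well". It also plans full listings, and "separate listings of data for chemistry, hematology, and urinalysis will be provided for each parameter where a subject had at least one abnormal result".

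**Which values enter the tables.** Under SAP 5.7, a retest result is the one used for summaries. Unscheduled safety measurements stay out of by-visit tables and are only listed. Early termination results appear as a separate visit.

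**Adverse-event outputs.** SAP 14.1 gives the number and percentage of subjects with TEAEs leading to treatment interruption, study drug discontinuation and study discontinuation, and with TEAEs of clinical interest. On when a laboratory result becomes an adverse event, Protocol 8.4.4 says: "Any clinically significant findings will be reported as an AE".

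**The concern.** The protocol defines in numbers which laboratory results require study drug to be interrupted or the subject to be discontinued. A reader of the report will want to know how many subjects on 40 mg, 80 mg and placebo reached each limit. Change in safety laboratory tests is a secondary safety endpoint, and SAP 14.1 treats neutropenia, lymphopenia, liver enzyme elevation and CPK elevation as events of clinical interest. Yet the laboratory section produces no such count.

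The handling rules in SAP 5.7 add to the gap. A subject who meets a 4.4.1 limit "will have the study drug interrupted until laboratory retesting is performed", so these are the subjects most likely to have a retest or an unscheduled sample. The by-visit tables are therefore least reliable for the values that matter most here. What is at stake is the completeness of the safety description. No efficacy result or inferential test is affected.

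**Working it through.** The plan states no figure to reproduce. The check compares each laboratory limit with every safety output in SAP 5.5, 5.7, 14.1 and 14.2.

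**Step 1. The limits and the planned counts** (cell counts in ×10³/µL)

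| Analyte | 4.4.1 interruption | 4.4.2 permanent discontinuation | Subject count against the limit | TEAE of clinical interest in SAP 14.1 |
|---|---|---|---|---|
| Neutrophils | >0.5 and <1 | ≤0.5 | none | neutropenia |
| Lymphocytes | >0.2 and <0.5 | ≤0.2 | none | lymphopenia |
| Platelets | >50 and <100 | ≤50 | none | none |
| CPK | >10 × ULN | – | none | CPK elevation, in one item with lipids |
| AST/ALT | >5 × ULN | – | none | liver enzyme elevation |

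Limits: 5 + 3 = 8. Planned counts: 0 of 8. Analyte groups with an adverse-event proxy on the clinical-interest list: 4 of 5. Platelets have none.

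**Step 2. Can the by-visit extremes supply the count?** A minimum beyond a limit shows that at least one subject crossed it at that visit, but not how many. Visits cannot be added up, because the same subject may recur. For CPK and AST/ALT the limit is a multiple of the ULN, and SAP 14.2 does not say that results will be expressed that way.

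**Step 3. Does the triggering value reach the by-visit table?** There are three routes under SAP 5.7:

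- It is found at a scheduled visit and then retested: the retest is summarised and the triggering value is not. The rule is not limited to screening.
- It is found at an unscheduled visit: it is left out.
- It is found at a scheduled visit and the follow-up sample is classed as unscheduled: the triggering value stays and may be the printed minimum or maximum.

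So it can be lost by two of the three routes and then appears only in a listing.

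**Step 4. Can the TEAE counts replace the table?** The TEAE terms have no numeric definition. The counts of TEAEs leading to interruption do not say which limit was met. An interruption driven by a laboratory value but not reported as an adverse event is not counted. SAP 11 summarises days treated and compliance, not interruptions, although Protocol 4.4 requires interruptions and their reasons in the case report form.

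**Step 5. Scale.** SAP 5.1 plans up to 35 subjects per group, so one subject is 1/35 = 2.9%. For a true per-subject crossing rate p, the chance of at least one crossing in an arm is 1 − (1 − p)^35. The rates are assumed, because the documents give none:

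| Assumed p | Chance of at least one crossing |
|---|---|
| 1% | 1 − 0.99^35 = 30% |
| 2% | 1 − 0.98^35 = 51% |
| 5% | 1 − 0.95^35 = 83% |

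At such rates a few individuals per arm would carry the whole comparison, so a count of subjects is the natural summary.

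**The case against.** The strongest defence is that the severe cases are already visible. Minimum and maximum are tabulated, so a very low neutrophil count would be printed for its arm and visit. Meeting a limit forces interruption or discontinuation, and the reasons must be recorded (Protocol 4.4). Where a subject is removed for a laboratory result, Protocol 7 requires the specific test to be recorded. SAP 7.1 tabulates reasons for study discontinuation, and SAP 14.1 counts TEAEs leading to interruption or discontinuation. Protocol 8.7.1 counts abnormal laboratory findings among possible adverse events, and an investigator is unlikely to call a value that forces withdrawal insignificant. A reported platelet event would appear in the tables by system organ class and preferred term. The listings allow a hand count, and the table shells, in a separate document not available here, may contain more.

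Much of this stands. A reader might infer that laboratory safety is summarised only by means, or that severe values can be found only in listings. SAP 5.5 and 14.1 contradict both. A reader might also infer that the shift tables are a two-way normal/abnormal split that puts trivial and severe values in one cell. The SAP does not define its shift categories, so this cannot be established.

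The defence does not produce the missing count. The extremes are subject to SAP 5.7 and carry no denominator. The adverse-event and disposition tables record consequences and reported events, not numeric crossings. The SAP text commits to no table of them.

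**Conclusion.** The point holds as a cheap improvement to the safety reporting. None of the eight laboratory limits has a planned per-arm subject count. The by-visit extremes and the TEAE counts are partial substitutes, and SAP 5.7 can remove the triggering value from the by-visit tables.

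This rests on the SAP text as written, on reading the retest rule as applying after baseline because nothing restricts it, and on the table shells adding nothing further. The chances in the scale illustration depend on assumed rates; the finding does not.

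A reader might extend the point to QTcF, because SAP 14.4 offers only a shift table "describing shifts to abnormality will be provided for overall interpretation". The documents do not support treating it the same way. The 450 ms figure in exclusion criterion 12 is a screening eligibility rule, and neither 4.4.1 nor 4.4.2 contains a QTcF limit. SAP 14.4 also gives descriptive statistics for QTcF, which include the maximum.

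**What to change.** Add one descriptive table to SAP 14.2, on the safety population:

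- **Rows:** each existing laboratory limit in Protocol 4.4.1 and 4.4.2, unchanged, with n (%) of subjects who have any post-baseline on-treatment value meeting it. A subject may count in more than one row.
- **Columns:** randomised arm for Part A; treatment received for Part B or for time on ASN002, using the Appendix 1 groupings so that placebo subjects who cross over are identifiable.
- **Values used:** scheduled, unscheduled and early termination results, and the initial result before any retest.
- **Rule:** state that the retest and unscheduled-visit rules of SAP 5.7 do not apply to this table.

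The cost is one table from data already collected, with no new assessment and no inferential test. The drawback is that a single unconfirmed or spurious value counts as a crossing; a footnote should say so, and the listings allow each case to be checked.
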